7.1.2 Serious Adverse Events

An SAE is any AE that results in one of the following outcomes:

- Death.
- Is life-threatening (the term “life-threatening” refers to an event in which the subject was at risk of death at the time of the event; it does not refer to an event which hypothetically might have caused death if it were more intense).
- Requires in-patient hospitalization (formal admission to a hospital for medical reasons for any length of time), or prolongs existing hospitalization.
- Results in a persistent or significant disability/incapacity, or substantial disruption of the ability to conduct normal life functions.

- Congenital anomaly/birth defect (in the child of a subject who was exposed to the study treatment).
- Other important medical event. Medical and scientific judgment should be exercised in determining whether an event is an important medical event. An important medical event may not be immediately life-threatening and/or result in death or hospitalization but required medical intervention in order to prevent a SAE outcome. However, if it is determined that the event may jeopardize the subject and/or may require intervention to prevent one of the other SAE outcomes, the important medical event should be reported as serious. Examples of such events are intensive treatment in an emergency room or at home for allergic bronchospasm; blood dyscrasias or convulsions that do not result in hospitalization; or development of drug dependency or drug abuse.

The following hospitalizations will not be considered SAEs:

- A visit to the emergency room or other hospital department for <24 hours that does not result in in-patient admission (unless considered an “important medical event” or a “life -threatening event”).
- Elective surgery or planned surgery prior to signing the ICF.
- Admissions as per protocol for a planned medical/surgical procedure.
- Routine health assessments requiring admission for Baseline/trending of health status (eg, routine colonoscopy).
- Medical/surgical admission for a purpose other than healthcare purposes and was planned prior to entry into the study (appropriate documentation is required in these cases).
- Admission encountered for another life circumstance that carries no bearing on health status and/or requires no medical/surgical intervention (eg, lack of housing, economic inadequacy, care-giver respite, family circumstances, administrative).
- Progressive disease (NPDR) is expected and will not be considered an SAE.

Clarification of SAEs:

- Death is an outcome of an AE, and not an AE in itself.
- All deaths, regardless of cause or relationship, must be reported.
- Complications that occur during hospitalizations are AEs. If a complication prolongs hospitalization, it is an SAE.
- “In-patient hospitalization” means the subject has been formally admitted to a hospital for medical reasons for any length of time. This may or may not be overnight. It does not include presentation to, and/or care within, an emergency department.
- The Investigator should attempt to establish a diagnosis of the event based on signs, symptoms, and/or other clinical information.

Note: Progressive disease should be recorded on the AE eCRF. However, because it is expected in the study population, it will not be considered as an SAE.

7.1.3 Sight-Threatening Ocular Events Defined as SAEs in This Study

In addition to the standard SAE categories described above, this study defines these additional ocular events as SAEs:

- An AE that causes a decrease in visual acuity of ≥ 30 letters or ≥ 6 lines from the most recent previous measurement of visual acuity, lasting more than 1 hour.
- An AE that causes a decrease in visual acuity to light perception or worse, lasting more than 1 hour.
- An AE that requires surgical intervention (eg, conventional surgery, vitreous tap, or biopsy with intravitreal injection of anti-infectives, or laser or retinal cryopexy with gas) to prevent permanent loss of sight.
- An AE that is associated with severe intraocular inflammation (ie, 4+ anterior chamber cell score or 4+ vitreous haze score).
- Two consecutive IOP measurements of ≥ 30 mmHg taken at least 72 hours apart when a subject is already being treated with two IOP-lowering medications.
- An IOP < 6 mmHg requiring medical intervention.
- An AE that in the opinion of the Investigator requires medical or surgical intervention to prevent permanent loss of sight.

The Investigator must employ all necessary therapeutic measures to resolve the SAE. Any medications or therapies used to treat the SAE must be recorded in the concomitant medication eCRF.

7.1.4 Clinical Laboratory Adverse Events

An abnormal laboratory result should be considered an AE if it:

- Results in the initiation or change of an intervention (eg, increased dose of medication), based on medical evaluation (eg, packed red cells for low hemoglobin).
- Results in any out of range laboratory value that in the Investigator's judgment fulfills the definitions of an AE.
- Increases in severity compared to baseline.

Abnormal laboratory values should not be listed as separate AEs if they are considered to be part of the clinical syndrome that is being reported as an AE. Any laboratory abnormality considered to constitute an AE should be reported on the AE eCRF. It is the responsibility of the Investigator to review all laboratory findings in all subjects and determine if they constitute an AE. Medical and scientific judgment should be exercised in deciding whether an isolated laboratory abnormality should be classified as an AE.

All laboratory AEs should be repeated and reassessed by the Investigator to track resolution and especially to confirm if they meet the definition of serious. If serious, they will be reported as SAEs.

The Investigator or a licensed designee must review all laboratory results in a timely manner as demonstrated by signature/date.

7.1.5 Adverse Event Severity and Relationship

Adverse event severity is defined as a qualitative assessment of the intensity of an AE as determined by the Investigator. The assessment of severity is made irrespective of the relationship or seriousness of the event to EYP-1901, sham, or the injection device.

In the absence of an assigned severity per the CTCAE version 5.0 or higher ([Appendix 4](#)) grading criteria, the Investigator will grade AEs according to the following severity criteria:

Mild/Grade 1: The event may be noticeable to subject; does not influence daily activities; usually does not require intervention.

Moderate/Grade 2: The event may be of sufficient severity to make subject uncomfortable; performance of daily activities may be influenced; intervention may be needed.

Severe/Grade 3: The event may cause severe discomfort; usually interferes with daily activities; subject may not be able to continue in the study; treatment or other intervention usually required.

Life- or Sight-Threatening/Grade 4: The event requires urgent intervention to preserve life and/or permanent loss of vision.

Death/Grade 5: The event resulted in the subject's death.

Causality/Relationship to Study Treatment

The relationship of study treatment (ie, EYP-1901 or sham), the applicator, or the injection procedure, to each AE must be determined by the Investigator according to the following:

Not Related: Evidence indicates no plausible direct relationship to the study treatment, device, or procedure, or there is a reasonable causal relationship between non-study product, concurrent disease, or circumstance and the AE; and/or a causal relationship is considered biologically implausible.

Possibly Related: There is a reasonable causal relationship between the study treatment, device, or procedure and the AE. There may or may not be a clinically-plausible temporal sequence between the onset of the AE and study treatment, device, or procedure; the AE is not reasonably supported by other conditions.

Probably Related: The study treatment, device, or procedure and AE occurrence are reasonably related in time; a clinically-plausible temporal sequence between the onset of the AE and study treatment, device, or procedure is likely; based upon the Investigator's clinical experience, the association of the AE with study treatment, device, or procedure is likely; all other potential causes have been ruled out.

If the relationship between the AE/SAE and the sequence study treatment, device, or procedure is determined to be "possible" or "probable", the event will be considered related for the purposes of expedited regulatory reporting.

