7.1 Adverse Events

The following are specific definitions of terms guided by the International Council for Harmonization of Technical Requirements for Pharmaceuticals for Human Use (ICH E2), Guidelines for Good Clinical Practice (GCP), and the US Code of Federal Regulations (CFR) that apply to the following sections. The severity of AEs will be graded by CTCAE version 5 or higher ([Appendix 4](#)).

Definition of Adverse Event:

An AE is defined as any new untoward medical occurrence or worsening of a pre-existing medical condition in a patient or clinical investigation subject administered an investigational or marketed (medicinal) product and that does not necessarily have a causal relationship with the product. An AE can therefore be any unfavorable and unintended sign (including an abnormal laboratory finding, for example), symptom, or disease temporally associated with the use of a medicinal product, whether or not considered related to the product.

AEs may also include pre- or post-treatment complications that occur as a result of protocol-specified procedures (eg, invasive procedures such as venipuncture, delivery procedure, etc.). Pre-existing conditions that increase in severity or change in nature during (or as a consequence of use of a medicinal product) the study will also be considered AEs.

An AE Will Not Include:

- Medical or surgical procedures (eg, surgery, endoscopy, tooth extraction, transfusion) for events that led to the procedure
- Pre-existing diseases, conditions, or laboratory abnormalities present or detected prior to the Screening Visit, unless they worsen during the study
- Situations where an AE or untoward medical occurrence has not occurred (eg, hospitalization for elective surgery, social and/or convenience admissions)

Associated with the Use of the Drug (Causality):

There is a reasonable possibility that the event may have been caused by the study medicinal product (and/or the administration procedures).

Unexpected Adverse Event:

Any event that is not identified in nature, severity, or frequency in the current version of the IB; or in the product labeling for marketed products. For example, if the IB or product labeling referred to elevated hepatic enzymes or hepatitis, then an event of hepatic necrosis would be considered unexpected by the virtue of the greater severity. The Sponsor or designee will determine AE expectedness.

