7.1.7.1 Reporting of Serious Adverse Events

All SAEs, regardless of cause(s) or relationship to study drugs, must be recorded on the appropriate eCRF page and reported to the Sponsor within 24 hours of the Investigator's first awareness using the study's designated SAE/SADR (Serious Adverse Drug Reaction) Report Form.

Minimal information to be provided on the SAE/SADR Report Form includes:

- Protocol number
- Site and Investigator identifiers

- Subject number
- Brief description of the event(s)
- Onset date of the event
- Outcome of the event as of the date of report, if known
- Resolution date and time, if the event(s) resolved
- Any medication administered to treat the event
- Investigator's assessment of the causal relationship of the SAE to the study medicinal product
- Additional and follow-up information as requested by Sponsor or its designee

SAEs must be reported using the study's designated SAE/SADR Report Form and sent to:

PPD [REDACTED]
[REDACTED]
[REDACTED]

The Investigator will also compile other relevant documentation with urgent priority (eg, copies of test results, hospital discharge summary, autopsy report, etc.), and send this information to the Sponsor (or Sponsor's designee).

The FDA and all participating Investigators shall be notified by a written Investigational New Drug Application (IND) safety report of any AE associated with the use of the investigational product that is both serious and unexpected no later than 15 calendar days from the Sponsor's awareness date of the event. An SAE is considered to be associated with the use of the investigational product if the relationship between the SAE and the investigational product is classified by the Investigator as "possibly related" or "probably related" (ie, suspected, unexpected serious adverse reaction [SUSAR]). Any unexpected fatal or life-threatening SAE associated with the use of the investigational product will be reported to the FDA by the Sponsor within 7 calendar days.

The IRB/EC should be notified of SAEs as required in accordance with the local institutional policy.

All Investigators participating in the study will be notified of unexpected SAEs determined to be related to study treatment/injection procedure.

Pregnancy

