### 11.1. Adverse Events

All AEs will be coded using the most recent version of MedDRA, version 25.0 or higher, and will be presented in the following data listings by SOC and PT for each subject.

- All AEs
- Ocular AEs
- AEs related to study treatment
- Serious adverse events (SAEs)
- SAEs related to study treatment
- AEs with an outcome of death
- AEs leading to study treatment discontinuation
- AEs leading to study withdrawal

Treatment-emergent adverse events (TEAEs) are AEs that began on or after the date of study treatment administration. Missing/incomplete start or stop dates associated with an adverse event (AE) will be handled as per [Section 8.3.2](#) to determine whether an AE is a TEAE. The following categories of TEAEs will be summarized by treatment arm and overall for the Safety Set using count and percentage of unique subjects experiencing a TEAE and number of events for each TEAE by SOC and PT. An overall summary table will also be produced to summarize the following categories of TEAEs.

- All TEAEs
- TEAEs related to study treatment
- Serious TEAEs
- Serious TEAEs related to study treatment
- TEAEs by maximum severity (mild [Grade 1], moderate [Grade 2], severe [Grade 3], life/sight-threatening [Grade 4], death [Grade 5]), total number of events at each severity summarized
- TEAEs by worst relationship (not related, possibly related, probably related), total number of events at each relationship summarized
- TEAEs leading to study treatment discontinuation
- TEAEs leading to study withdrawal

Summaries will be presented separately by location of the TEAEs (ocular in study eye, ocular in non-study eye, and non-ocular), and will be sorted by overall descending count of SOC and then, within a SOC, by overall descending count of PT. Subjects will only be counted once if they experience multiple events under the same SOC or PT, and at the maximum severity or worst relationship, as applicable.

This document is confidential.

Summaries by SOC and PT (not by maximum severity or worst relationship) will also include a summarization of the number and percentage of subjects with more than 1 TEAE.

Summaries of TEAEs (ocular in study eye, ocular in non-study eye, and non-ocular) by PT only will be presented by treatment arm and overall, sorted by overall descending count of PT. Subjects will only be counted once if they experience multiple events under the same PT.

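### The causality categories in Protocol 7.1.5 have no related category for an event that either the study treatment or concurrent disease could reasonably have caused, contradicting the causality standard in Protocol 7.1

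*Protocol*

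**What the plan says.** Protocol section 7.1 gives a general definition of association with the drug: "There is a reasonable possibility that the event may have been caused by the study medicinal product". It extends this to the administration procedures and makes no exception for events that have another possible cause.

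Protocol section 7.1.5 then requires the investigator to assign one of three categories.

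- **Not Related** has alternative limbs. One is that there is no plausible direct relationship to the treatment, device or procedure. Another, joined by an *or*, is that "there is a reasonable causal relationship between non-study product, concurrent disease, or circumstance and the AE".
- **Possibly Related** requires a reasonable causal relationship with the treatment, device or procedure. It ends with the condition that "the AE is not reasonably supported by other conditions".
- **Probably Related** requires, among other things, that "all other potential causes have been ruled out".

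These categories have two uses downstream. For reporting, section 7.1.5 says that after a possible or probable assessment "the event will be considered related for the purposes of expedited regulatory reporting". Section 7.1.7.1 treats an SAE as associated with the product "if the relationship between the SAE and the investigational product is classified by the Investigator as" possibly or probably related. For analysis, SAP section 11.1 tabulates "TEAEs related to study treatment", the serious related TEAEs, and TEAEs by worst relationship on the same three categories.

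**The concern.** Sections 7.1 and 7.1.5 apply different tests to the same question. The first asks whether the product may reasonably have caused the event. The second in effect also asks whether anything else reasonably could have, and if so sends the event to Not Related.

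This matters more than usual here. Every subject has diabetes and a study eye with moderately severe to severe NPDR. Protocol section 1.2 lists CI-DME, tractional retinal detachment, epiretinal membrane and vitreous hemorrhage as common complications of that disease. If one of these follows an intravitreal injection, the concurrent disease will often be a candidate explanation.

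Two things are at stake: whether the related-TEAE tables describe relatedness by the protocol's own standard, and whether a serious unexpected event that meets that standard enters the expedited route.

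**Working it through.** There is no figure in the plan to reproduce, so the check is logical. Classify an event by two yes/no judgements: could the treatment, device or procedure reasonably have caused it, and does another disease or circumstance have a reasonable causal relationship to it? Then apply each definition.

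| Treatment cause reasonable | Other cause reasonable | Section 7.1 standard | Section 7.1.5 category |
|---|---|---|---|
| Yes | No | Associated | Possibly or Probably Related |
| Yes | Yes | Associated | Not Related |
| No | Yes | Not associated | Not Related |
| No | No | Not associated | Not Related |

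The two sections agree in three rows and conflict in the second. For that row, step by step:

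1. *Probably Related* fails, because the other cause has not been ruled out.
2. *Possibly Related* fails. Its first clause is met, but its last is not, since another condition reasonably supports the event. The relaxation in that definition (that something may or may not be present) concerns timing only and does not reach the last clause.
3. *Not Related* is met through the limb on concurrent disease or circumstance. That limb follows an *or*, so the investigator does not have to find the treatment implausible.

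The consequences follow from the other sections.

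4. *Expedited reporting.* Sections 7.1.5 and 7.1.7.1 both key on the investigator's possible or probable category, so a row-two event does not meet the stated trigger. The determination that section 7.1 assigns to the sponsor is expectedness. No sponsor upgrade of causality is described.
5. *Tables.* SAP section 11.1 does not say which categories count as related. Possibly plus probably is the natural inference from Protocol 7.1.5. On any reading, a Not Related event is left out of the related-TEAE and related serious TEAE tables.
6. *Outputs not affected.* Protocol 11.4.7 and SAP 11.1 summarize all TEAEs by arm, including sham, and serious TEAEs whatever the relationship. The safety endpoint in SAP 5.4 is the rate of all TEAEs. Section 7.1.7.1 sends every SAE to the sponsor within 24 hours regardless of relationship.

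The share of row-two events among all events possibly caused by treatment cannot be derived. The documents give no adverse event rates and nothing on how often an alternative cause would be judged reasonable.

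**The case against.** The strongest reply is that this is loose drafting with limited reach. Its parts carry different weight.

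- *The threshold is not trivial.* The Not Related limb needs a reasonable causal relationship between the other condition and the particular event. Having diabetes does not satisfy it automatically. This stands: the rule does not remove every event in a diabetic subject, only those where the investigator judges the other cause reasonable.
- *A row-two event also meets the first clause of Possibly Related,* and section 7.1 supplies the general standard, so an investigator might still choose that category. Some may. But the last clause of Possibly Related points the other way, and investigators are told to follow the categories. Leaving sites to choose between two tests is itself the defect.
- *The sponsor sees everything.* All SAEs reach the sponsor, and Protocol section 7 has the sponsor reviewing all TEAEs under a Safety Management Plan that is not among these documents. A reader might infer that the sponsor cannot recover a misclassified event. The text does not support that: it says an event is associated if it is so classified, not only if. What can be said is that no sponsor route is described.
- *Many safety events have no ready diabetic explanation.* The ocular AE and SAE lists in 7.1.1 and 7.1.3 include anterior chamber cells, vitreous haze and raised or low IOP. Prior intraocular inflammation, uveitis and uncontrolled ocular hypertension or glaucoma are excluded at entry. Section 7.1.2 also says that progressive NPDR is not an SAE, which limits the effect on expedited reporting for progression. This stands, so a claim that most events of interest are affected would go too far. The supported examples are the complications named in section 1.2.
- *The randomized comparison is intact.* This stands. The all-causality comparison with sham does not depend on attribution. With about 20 subjects per arm it resolves only large differences, so it does not fully replace case-level causality. For illustration, 4/20 against 0/20 gives a two-sided Fisher p of 2 × C(20,4)/C(40,4) = 2 × 4,845/91,390 = 0.11. The plan is descriptive and does not run this test.

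**Conclusion.** The point holds as a contradiction within the protocol. Section 7.1.5, as worded, classes as Not Related an event that section 7.1 counts as associated with the drug, whenever another cause is also reasonable. Events possibly caused by the drug or the procedure that diabetic eye disease could also explain can therefore be left out of the related-TEAE tables and of the stated expedited-reporting trigger.

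The conclusion assumes that sites apply the 7.1.5 definitions literally and, for the tables, that related means possibly or probably related. It does not show that drug-caused events will in fact be lost, or how many. Any percentage would only restate an assumption about how often a second cause is judged reasonable. The all-causality safety endpoint, the comparison with sham and SAE submission to the sponsor are untouched. The correction is still needed, because the conflict sits in the rule that decides which serious events count as associated with the product.

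**What to change.** Bring Protocol section 7.1.5 into line with section 7.1.

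1. In Not Related, delete the limb on an alternative cause, so that the category means there is no reasonable possibility that the treatment, applicator or procedure caused the event.
2. In Possibly Related, replace the final condition with wording that lets the category apply even if another cause is also plausible.
3. Optionally, state in section 7.1.7.1 whether the sponsor's own causality assessment can also make an SAE associated with the product. The protocol is silent on this, so it would add a process rather than correct an error.

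The cost is a protocol wording change and matching eCRF completion guidance. The planned SAP tables can stay as they are. The downside is that somewhat more events will be classed as related, and somewhat more SAEs will be assessed for expedited reporting.
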